3.2. Inclusion Criteria

- 1. High risk prostate cancer¹ with no detectable distant metastasis using standard of care imaging (MRI prostate/pelvis, isotope bone scan, CT, non-PSMA PET/CT) undergoing radical prostatectomy and pelvic lymph node dissection.
- 2. ⁶⁸Ga-PSMA PET/CT done as part of the staging investigation
- 3. Histologically proven prostate cancer.
- 4. No prior prostate cancer treatment including androgen deprivation therapy.
- 5. Male aged 18 or over.
- 6. Considered suitable candidate for radical surgery for prostate cancer.
- 7. Willingness to comply with scheduled visits

3.3. Exclusion Criteria

- Evidence of demonstrable distant metastasis on standard of care imaging using combination of MRI, CT, isotopic bone scan, non-PSMA PET/CT, or PSMA-PET/CT where undertaken as standard of care.
- 2. Patients not willing to receive surgical treatment with radical prostatectomy and pelvic node dissection.
- 3. Patients who are unable or unwilling to give informed consent.

3.4. Withdrawal of Subjects

Patients withdrawing from the study for reasons such as safety, non-compliance or withdrawal of consent etc will continue to be followed up for efficacy and safety as per protocol, unless they are lost to follow up, deceased or withdraw consent to the study.

¹ As defined by with NCCN high-risk prostate cancer, as defined by one or more of the following: PSA ≥20ug/L, Gleason sum score ≥8 or T-stage ≥ c T3

Patients may *withdraw* from the study at any point; this should be indicated on the deviation case report form (CRF).

3.5. Endpoints

Primary Outcomes:

- 1. To establish whether prostate tumours with high PSMA expression have enhanced risk of pelvic nodal metastasis.
- 2. To establish best practice and optimise protocols for multi-centre application of PSMA PET/CT imaging.

Secondary Outcomes:

- 1. To evaluate the feasibility of a future large scale randomised controlled trial (RCT), and develop quality assurance measures across the study team/network.
- 2. To develop a platform to carry out RCT to study the usefulness of novel imaging/biomarkers for evidence-based treatment decisions in patients at risk of pelvic nodal prostate cancer.

4. TREATMENT

4.1. Treatment Schedule

Patients recruited into the trial will undergo no additional scans, tests or visits other than their normal routine care. Surgery is part of the routine clinical management of these patients and patients will have discussed surgery for their prostate cancer.

4.2. Concomitant Therapy

This study will not be collecting concomitant medications as this study is an imaging study only. Concomitant medications would not have any direct implications to the outcome of PSMA based imaging.

5. ASSESSMENT OF EFFICACY

5.1Treatment and Examination Schedule

Activity	SCREENING/BASELINE ^{a,}	SURGERY	FOLLOW UPb 6 weeks post surgery as per clinical practice
Written or verbal Informed consent	X		
Weight	X		
Eligibility checklist	X		
Study enrolment	X		
Radical Prostatectomy and Lymph Node Dissection		Х	
Outcome of surgery			X

^aScreening/baseline – Prostate Cancer has been diagnosed and confirmed by clinical, radiological and histological investigations pre operatively including relevant standard care.of imaging. Between decision for surgery and pre-operative assessment (to allow patient time for isolation in COVID-19 compliant manner).

^bFollow up clinic visit 6 weeks post operatively – the patient will receive the outcome of their surgery per routine clinical practice/indication. In current COVID-19 practice, follow up of patients may be via telephone consultation. Per local clinical practice, PSA test may be carried in local GP surgery.

5.2 Schedule of assessments

5.2.1. Screening/Baseline Procedures

Screening procedures.

- Clinical assessment
 - Signed informed consent or verbal consent (for patients who are unable to be seen in clinic prior to surgery
 - Weight
- Histological confirmation of prostate cancer by Prostatic biopsies.
- Laboratory determinations
 - o PSA.
- Radiological assessment confirmation of non-metastatic prostate cancer by
 - MRI prostate/ pelvis
 - o CT scan
 - o ⁶⁸Ga-HBED-PSMA-11 PET/CT scan (in lieu of Isotope bone scan)
 - Non- PSMA PET scan [e.g. ¹¹C-Choline PET scan, ¹⁸F-fluorodeoxyglucose (¹⁸F-FDG) FDG PET scan].
- Eligibility assessment checklist
- Study enrolment

Study Enrolment

The participant's research nurse and/or doctor will screen the participant to ensure that they meet the trial eligibility criteria.

Patients will be enrolled centrally with the Scottish Clinical Trials Research Unit (SCTRU). An eligibility and enrolment checklist must be completed prior to enrolment. Enrolment should take place within 6 weeks prior to the planned surgery.

Once consent has been obtained the participant should be enrolled by emailing the

PANORAMA team at the Scottish Clinical Trials Research Unit:

SCTRU email: [contact]

The following information will be required at enrolment:

- Name of hospital, consultant and person enrolling the patient
- Confirmation that the patient has given written or verbal informed consent for trial participation
- Confirmation that the patient is eligible for the trial by completion of the eligibility checklist
- Patients initials, date of birth and study ID number

SCTRU will send sites a Screening Log with a site specific number and sequential study ID numbers. This will be completed by sites as patients are enrolled in the study.

Following written or verbal informed consent being obtained from the patient, the site will inform the respective General Practitioner (GP) of the participant's enrolment.

It may be possible for participants to be recruited into other clinical trials, but this should be discussed with the OCI via SCTRU before this is considered.

PSMA PET/CT Imaging

PSMA PET/CT scans will be performed in centres accredited by the UK PET Core Lab, based at St Thomas' Hospital, London [www.ncri-pet.org.uk/]. Local protocols for scanning preparation, acquisition and quality control processes will have been reviewed to ensure they meet the minimum requirements for participation in the study.

PET scans will be collated by the UK PET Core Lab and technical checks will be undertaken to ensure the image data quality is acceptable and that the PSMA PET/CT scan has been performed to an acceptable standard prior to central review. Any scans not fulfilling these requirements will be flagged to the PI and Clinical PET Expert.

Within each participating NHS site, the study imaging data will remain within the site and stored on NHS computers in keeping with the site's information governance policies. To allow intercomparison of results from different centres, sites will be requested to store the raw image data to allow centralised reprocessing using standard parameters.

All imaging data will be pseudo-anonymised prior to transfer to the UK PET Core Lab (using patient initials and trial number) and sent in DICOM format. Transfer of scan images, raw data and reports will be performed electronically wherever possible. Where sites are unable to send data electronically, use of CDs / DVDs will be used. Electronic transfer from the scaning centres to the UK PET Core Lab will be done using MIMcloud, a cloud-based server located in the EU. Data transfer methods use secure transfer protocols with password protection features and encryption. The pseudo-anonymized data collected will be maintained on university computers and in a secure webhosted environment with password protection features and encryption.

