1.2. Pre-Clinical Data

Prostate-specific membrane antigen (PSMA) is a cell surface protein with significantly increased expression in prostate cancer cells when compared to other PSMA-expressing tissues such as kidney, proximal small intestine or salivary glands [3, 4]. Another advantage of PSMA as an imaging target is its transmembrane location with a large extracellular domain. Scintigraphy using ProstaScint® (antibody capromab pendetide) has been limited to the detection of non-viable tumor cells, as it targets the cytoplasmic PSMA domain. Other limitations of antibody-based tumor detection methods include their relatively long circulation time, leading to high background to signal ratios and subsequent reduced detection rates.

Methods have been developed to label PSMA ligands with ⁶⁸Ga, ⁹⁹mTc and ^{123/124/131}I, enabling their use for PET imaging, more scintigraphy options and radioligand therapy. The initial experience with PET/CT using (Glu-NH-CO-NH-Lys-(Ahx)-[68Ga (HBED-CC)] coupled to a binding motif to the extracellular domain of PSMA (referred to as 68Ga-HBED-PSMA thereafter) suggests its ability to detect recurrent prostate cancer as well as metastatic disease [5, 6, 7, 8]. The majority of reported literature with the use of PSMA based imaging utilised 68Ga-HBED-PSMA-11 as a highly specific tracer for PSMA. Increasingly 68Ga-HBED-PSMA-11 PET imaging is adopted in staging of patients with high risk primary and recurrent prostate

cancer. However, there is urgent need to obtain robust data from multi-centre prospective patients with intermediate to high risk prostate cancer. Importantly, none of the reported series on the use of PSMA PET incorporate formal benchmarking of a centralised PET reporting reference in their study design.

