Images from ⁶⁸Ga-PSMA PET/CT scanning will be interpreted by two experienced nuclear medicine physicians (one at the local scanning site as well as central reporting by an expert nominated from the PSMA imaging subgroup). All LNs with increased ⁶⁸Ga-PSMA accumulation will be assigned to their respective anatomical location, measured in the short axis, along with an assigned SUVmax for each affected LN. In addition, visual analysis of the ⁶⁸Ga-PSMA uptake will included a four-point certainty scoring scale (definitely negative, equivocal probably negative, equivocal probably positive, definitely positive). Although not our primary research focus, PSMA +ve lesions within the prostate will be categorised as either focal or diffuse. Disease involving only one of the four prostatic quadrants will be considered as focal. If prostatic lesions are detected in more than one quadrant, the disease will be classified as diffuse/multifocal (if non-contiguous). Signals that indicate potential distant metastatic sites will also be scored using the four-point certainty scoring scale as described above for pelvic nodes [13].

Attention will be paid to ensure comparable imaging protocols are used across participating sites to ensure data obtained are suitable for objective and robust reporting of PSMA PET/CT across the study. Lesion uptake will be categorised according to a predefined anatomical scoring template.

Image scoring

Interpretation of PET imaging will be performed in accordance with the NCRI PET framework. All positive LNs on ⁶⁸Ga-PSMA PET/CT will be assigned to the respective anatomical region: left/right external iliac; left/right internal iliac, left/right obturator; left/right fossa of Marcille. Positive matching will be defined as the correlation between PET scan positivity and histological positivity, with histopathological analysis of the LNs considered the reference standard. Positive nodes in each nodal region/chain will be scored individually. These data can then be analysed separately or collectively for each nodal region. Once recruiting sites have satisfied QC evaluation by the UK PET Core Lab, the SUV values will be generated by identical (or very similar) reconstruction algorithms and are expected to be reproducible across the study.

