9.3. Analysis Plan

A binary logistic regression model will be trained on the SUV values obtained from the PSMA PET/CT imaging to predict whether metastatic disease is present or not. The analysis will be carried out on a (i) per-patient, (ii) bilateral side, (iii) LN-region, and (iv) LN-specific basis (as previously described by Leeuwen et al [9]). Where necessary, a generalized estimating equation model will be used to adjust for correlations within regions of each patient. Performance on unseen data will be assessed using 10-fold cross validation, and calculating sensitivity, specificity, positive predictive value (PPV) and negative predictive value (NPV). The "gold standard" assessments to which the model predictions will be compared will be provided by pathology.

Comparison of PSMA PET/CT reporting between local nuclear physician evaluation and review by central experts will be represented in a Bland Altman plot. A consensus will be developed in terms of minimum training required for local nuclear physicians in the review of PSMA PET signals.

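### Independence of the central PET read is not secured: reports are transferred in the step that supplies the Core Lab, and nothing masks the central reader to the local report

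*Protocol*

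**What the plan says.** Section 3.1 (PSMA PET imaging and reporting) has each scan interpreted by two nuclear medicine physicians: "one at the local scanning site as well as central reporting by an expert nominated from the PSMA imaging subgroup". Neither is described as masked, blinded or independent of the other.

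Section 5.2.1 (PSMA PET/CT Imaging) describes what happens before central review. The Core Lab collates the scans, and "technical checks will be undertaken to ensure the image data quality is acceptable". On de-identification it says: "All imaging data will be pseudo-anonymised prior to transfer to the UK PET Core Lab (using patient initials and trial number"). The same paragraph then states: "Transfer of scan images, raw data and reports will be performed electronically wherever possible".

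Section 9.3 sets up the comparison: "Comparison of PSMA PET/CT reporting between local nuclear physician evaluation and review by central experts will be represented in a Bland Altman plot". It continues: "A consensus will be developed in terms of minimum training required for local nuclear physicians in the review of PSMA PET signals".

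Section 1.2 explains why the central read matters to this study. It says of earlier work that "none of the reported series on the use of PSMA PET incorporate formal benchmarking of a centralised PET reporting reference in their study design". Section 1.4 offers standardised reporting with central review as the remedy. Best practice for multi-centre PSMA PET/CT is the second primary outcome (sections 2 and 3.5).

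For nodal status, section 3.1 compares PET with pathology, "with histopathological analysis of the LNs considered the reference standard". Section 8.1 lists the histopathology outcome among the data collected by the Scottish Clinical Trials Research Unit (SCTRU).

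**The concern.** A comparison of two readers measures reading quality only if the second reader forms a view without the first reader's answer. Here the described data flow includes reports, the sender is the site, and the local report is the only kind of report that the text shows to exist at that stage. If the report is in front of the central reader, some central calls will follow it. The two sets of readings then agree more closely than independent readings would.

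What is at stake is the second primary outcome. The local-central comparison stands next to the decision on minimum training for local readers. Agreement that is partly borrowed would make local reading look better than it is and lead to a training requirement that is too light. It would also weaken the claim to provide the central benchmark that section 1.2 finds missing elsewhere.

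This is a matter of conduct, so the statistical analysis plan (not at hand) is not the place to solve it. Once a central read has been made with the local report in view, no later analysis can make it independent.

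**Working it through.** **No figure to reproduce.** The protocol states no expected agreement, and its sample size of 60 comes without a precision target for the comparison. The check is a reading of the text, followed by an illustration of size.

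**Step 1: which safeguards stand between the local report and the central reader?**

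| Step in the protocol | What it does | Does it hide the local interpretation? |
|---|---|---|
| Pseudo-anonymisation (5.2.1) | Replaces patient identity by initials and trial number | No |
| Technical checks (5.2.1) | Confirm image quality and scan standard | No |
| Two readers (3.1) | Names a local and a central reader | No masking or order stated |
| Comparison (9.3) | Plots local against central reading | No condition on how the reads are made |

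The word independent is used for the data monitoring committee and its members, the steering committee chair and the ethics committee. It is never used for the readers.

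**Step 2: is the order of central read and histology fixed?** The scan belongs to pre-operative staging (section 3.2), so the local clinical read should normally precede pathology. No time limit is set for the central read. Section 3.1 has the node dissection follow the template whatever the PET shows, so nothing in the workflow requires a central read before surgery. Against this, specimens are processed at the sites (5.2.2) and the result goes to SCTRU (8.1). No route to the Core Lab or the central reader is described.

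**Step 3: size, as an illustration.** These assumptions are not in the protocol:

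- Independent reads would differ by an amount D with mean 0 and standard deviation s.
- A share c of central values simply repeats the local value, so the difference there is 0. Which values are copied does not depend on D.

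The variance of the observed differences is then (1-c) × s² + c × 0 = (1-c) × s². The standard deviation, and with it the width of the Bland-Altman limits, is multiplied by sqrt(1-c):

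- c = 0.1: sqrt(0.9) = 0.95
- c = 0.3: sqrt(0.7) = 0.84
- c = 0.5: sqrt(0.5) = 0.71

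If local and central readings differ on average, copying also pulls the observed mean difference towards zero, by the factor 1-c. The simple square-root factor for the limits then no longer applies exactly.

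**The case against.** The strongest reply is that the text does not say what a reader might infer from it.

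- **Local reports reaching the reader.** A reader might conclude that the central reader is handed the local report. Section 5.2.1 says only reports. It does not call them local, and it does not say that the Core Lab passes them on. Receipt by the lab is not release to the reader. This stands: the text shows that independence is not secured, not that it is lost.
- **Histology.** A reader might also infer that the central read is informed by the reference standard. The documents describe no path for this. The most they support is that it is not excluded.
- **Effect on the primary model.** It is tempting to add that sensitivity and positive predictive value will be inflated. Section 9.3 trains the model on SUV values and does not say which reader's values are used. Section 3.1 presents SUVmax as an objective measure. Selecting nodes and assigning them to regions still depends on the reader, but an effect on the model is conditional and not shown.
- **A kappa statement.** One might express the bias as a rise in kappa. The plan is a Bland-Altman plot, and kappa depends heavily on the share of positive scans. In the background series of section 1.3, 4 of 30 patients were PET-positive (4 true positives at 100% specificity), or 13%. With both readers at that rate, chance agreement is 0.13² + 0.87² = about 0.77, and 80% raw agreement gives kappa (0.80 - 0.77)/(1 - 0.77) = about 0.13. Kappa figures based on balanced margins would not fit this setting.
- **An outside framework.** Section 3.1 refers to the NCRI PET framework for interpretation. It may contain masking rules, but the protocol does not cite it for that purpose and it is not at hand.

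These points narrow the concern. They do not supply the missing safeguard for the local-central comparison.

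**Conclusion.** The concern holds in a limited form. The protocol transfers reports in the step that supplies the Core Lab before central review, plans a local-central comparison alongside the setting of training needs, and nowhere masks the central reader or orders the reads.

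The direction of any bias is clear: if the local report is seen, agreement is overstated and training need understated. Its size is unknown. Under the copying assumption with zero mean difference, the limits would be 5% narrower at c = 0.1 and 16% narrower at c = 0.3. The effect should be weaker for SUVmax than for the four-point certainty score, because the latter is a judgement.

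Exposure of the central reader to histology is an open possibility only. No conclusion about the diagnostic accuracy of the SUV model follows. This is a cheap improvement to conduct that is worth making before central reads begin.

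**What to change.** 1. In section 5.2.1, state that only images and raw data are available to the central reader, and that the local report is released after the central read form is locked.
2. In section 3.1, state that the central reader is masked to the local read and to histology, and that any consensus is reached only after both reads are recorded.
3. Log the date of each central read and the date of the histology result, so that the order can be shown.

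If the PET framework already contains such rules, a reference to them at these two places would serve for the parts they cover.

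No extra reader, scan or patient is needed. The cost is a few sentences in the protocol and a little coordination at the Core Lab, which has to hold the reports back until the form is locked.

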5.2.2 Surgery - Radical Prostatectomy and Pelvic Node Dissection

Pathology

Surgical specimens from radical prostatectomy (RP) and pelvic node dissection will be processed at each of the participating centres for histopathological examination in line with the International Society of Urological Pathology (ISUP) consensus conference [11] and the UK Royal College of Pathologists (RCPath) dataset [12] by designated uropathologists.

Lymphatic tissue will be examined by palpation, visual inspection and sectioning at 3 mm intervals, in accordance with a consensus protocol within this study. The transversely sliced lymph nodes (LNs) will be processed, paraffin-embedded and histological sections cut and stained for Haematoxylin and Eosin (H&E). Disease positivity will be defined as the presence of any metastatic deposits of prostate cancer in the LNs examined. For each metastatic LN, both the short axis and largest diameter (expressed in mm) of the metastatic deposits will be

recorded. The number of positive nodes and the total number of nodes found will be reported for each of the nodal specimens submitted.

5.2.3. Follow up – post surgery

As part of routine clinical care, follow up 6 weeks after surgery.

- Clinical assessment
 - Outcome of surgery
 - Histopathology evaluation of surgical specimens
 - Post-op bloods per routine clinical practice PSA

6. Sub-Studies

Formal translational study and considerations into quality of life and health economics will be developed in a future randomised controlled trial if PSMA PET/CT is shown to be adequately specific and sensitive.

7. PHARMACOVIGILANCE

7.1. Adverse Events

Adverse Events will be not collected as all the treatment is standard patient care and there will be no administration of research treatment. Therefore, there will be no requirement to report Adverse Events or Serious Adverse Events. As there is no research treatment, any serious adverse event cannot be assessed as "related" or "unexpected" and there are no expected outcomes listed in the protocol.

7.2. Pregnancies

N/A

8. DATA MANAGEMENT

All data will be handled, computerised and stored in accordance with the GDPR and Data Protection Legislation and PHS Data Protection Policy.

